### SZMU0011 Version 3.0

# Rainbow Acoustic Monitoring (RAM) in Patients Weighing up to 10 kg Comparison Study

#### 1 INTRODUCTION

This document is a clinical investigational plan for a human research study. The study will be conducted in accordance with the ethical principles that have their origin in the Declaration of Helsinki. By participating in the study, the Investigator agrees to adhere to all stipulations of this protocol, the conditions of IRB approval, federal and local regulatory requirements, 21CFR 812, ISO-14155 and International Conference on Harmonization Good Clinical Practice guidance ICH GCP.

#### 1.1 Background and Rationale

Recording vital signs (pulse rate, respiratory rate, blood pressure and temperature) is the standard of care for all patients on the hospital ward. However, documentation of vital signs is often poor or inaccurate. Of the four vital signs, respiratory rate is particularly difficult to assess and often not recorded in the patient record. This is in spite of the fact that elevated respiratory rate is one of the best predictors of respiratory deterioration, cardiac arrest and admission to the intensive care unit (ICU).

[figure not shown]
A simple noninvasive device to continuously monitor respiratory rate is therefore highly desirable. However, existing automated methods have had limited success in broad adoption due to either low accuracy leading to too many false alarms or due to poor patient tolerance for continuous monitoring. These current methods include impedance pneumography (taken from standard ECG electrodes) and end-tidal carbon dioxide monitoring that utilizes a special nasal cannula to sample respiratory gases. The former suffers from low accuracy resulting in high false alarm rates . In addition, impedance pneumography is a measure of respiratory effort and is known not to detect obstructive apneas, a major requirement for continuous surveillance monitoring of at risk patients. Capnography (ETCO2) monitoring is commonly used in the operating room/anesthesia setting but is not well tolerated in other patient care areas due to patient wearability issues that have resulted in limited compliance.

These limitations led Masimo Corporation to develop the rainbow Acoustic Monitoring (RAM) system with Masimo's Signal Extraction Technology (SET®). RAM noninvasively and continuously monitors and measures the acoustic respiration rates (RRa) and waveforms using an adhesive sensor with an integrated acoustic transducer converting acoustical airflow patterns to respiration rates. The RRa has shown to be accurate and reliable in offering clinical facilitations in early detection of respiratory compromise and patient distress in comparison to capnography monitoring .

The rainbow acoustic respiration sensor (RAS)-125c, is a FDA-cleared RAM sensor which can be applied to adult and pediatric patients weighing greater than 10 kg. The investigational RAM sensor is smaller in design compared to RAS-125c to facilitate sensor placement and improve attachment to the patient's neck with a transparent adhesive to allow flexibility upon sensor placement. The investigational RAM sensor is similar to the RAS-125c in performance parameters but differs in shape and size. In this study, the investigational RAM sensor is being evaluated for use in subjects up to 10 kg.

#### 1.2 Investigational Devices

Masimo's RRa is a parameter that uses an integrated acoustic transducer to convert the acoustical airflow patterns and waveforms from the rainbow® Acoustic Respiration Sensors (RAS), also known as RAM sensors, to calculate respiration rates. Disposable single-use investigational RAM sensors will be evaluated in subjects up to 10 kg and is intended to measure non-invasive acoustic respiration rates.

[figure not shown]

Figure 1. The small and round INVSESNOR00004 sensor (left) and the corresponding sensor placements around neck and chest regions (right).

The investigational use of the investigational RAM sensor for subjects up to 10 kg has undergone risk analysis and safety testing in accordance with applicable safety standards, including electrical safety, current leakage, mechanical safety and biocompatibility testing for patient contacting materials. The risk analysis conducted resulted in the investigational sensor being classified as a low risk device.

#### 2 STUDY DEVICES

#### 2.1 Description

#### **Investigational Devices:**

#### INVSENSOR00004:

The investigational INVSENSOR00004 rainbow acoustic monitoring (RAM) acoustic respiration sensor is designed to noninvasively convert acoustical airflow patterns into respiratory rate (RRa).

The investigational sensor is a single patient use adhesive sensor which includes biocompatible materials suitable for continuous skin contact.

Masimo Radical 7 pulse co-oximeter:

The Radical-7 is an FDA-cleared device, however that enables the use of the investigational sensor for monitoring on the pediatric population, changing its status to an investigational device. No new patient risks will be introduced by the addition of the new software.

#### FDA-cleared:

Masimo pulse oximeter sensor and RAM Dual patient cable:

The pulse oximetry sensor is FDA-cleared and will be used along with the investigational RAM sensor. Pulse oximetry sensors function by shining light through the fingers or toes of the patient per manufacturer's directions for use to detect pulsation in the capillaries. The RAM dual patient cable joins connection to the investigational RAM sensor.

Capnostream capnography:

The Capnostream capnography is FDA-cleared device that monitors concentration of carbon dioxide (CO2) in exhaled air to determine end-tidal CO2 (EtCO2) during anesthesia and intensive care. The capnography utilizes a mask or nasal cannula that is placed at the nostrils of the patient to detect breathing and airflow.

#### Reference analyzers/methods:

The acoustic raw data collected by the INVSENSOR00004 sensor and Radical 7 pulse co-oximeter will be manually annotated to obtain the inspirations and expirations by sound and visual measurements. The reference (RRref) will be obtained by measuring respiration rate based on the manual annotations of respiratory inspirations and expirations.

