#### 3 STUDY OBJECTIVES

The objective of this clinical investigational study is to compare the acoustic respiration rates (RRa) obtained using the INVSENSOR0004 sensor in the subjects up to 10 kg with the respiration rates determined by manual annotations (RRref), and when applicable with capnography respiration rate (RRcap).

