#### 4 STUDY DESIGN

#### 4.1 General Design

This is a multi-center, prospective and nonrandomized study design. RRa measurements will be compared to measurements of actual respiration rates as determined by manual annotation of recorded respiration data, and when applicable to capnography data.

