#### 4.2 Study Outcome and Measurement

Evaluation on the comparison of RRa measurements will be reported as a bias of between the acoustic respiration rate (RRa) parameter and the manual annotation (RRref).

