- 7.2.4 The investigational INVSENSOR00004 sensor and pulse oximeter sensor will both be connected to the RAM Dual patient cable. The patient cable is connected into the Radical 7 pulse co-oximeter.
- 7.2.5 Research study staff will assess if the subject can tolerate the capnography mask or nose sensor prior to recording data. The capnography sensor is connected into the Capnostream capnography.
- 7.2.5.1 If the subject is not able to tolerate with the capnography sensor then the capnography data will not be recorded.
- 7.2.6 Data will be recorded using laptop with the
- 7.2.7 Periodic checks will be made to ensure subject's well-being and tolerance of the sensors, and to check that sensors are connected. Refer to Procedure Manual for data collection details.
- 7.2.8 Periodic checks are to be performed at a frequency that is determined to be suitable by the PI and designated study staff
- 7.2.9 A minimum of manual breath-counts with the duration of each count will be performed at the start and towards the end of data collection. All measurements will be recorded in the CRF.
- 7.2.9.1 Additional manual breath counts ( duration) may be obtained depending on the length of the data collection period.
- 7.2.10 The length of the noninvasive INVSENSOR00004 sensor and pulse oximeter sensor readings will be a minimum of
- 7.2.11 Once the subject completes data collection or if the subject withdraws early prior to study completion, the sensors will be removed and the skin will be inspected for signs of redness or irritation. Any skin irritations will be recorded in the CRF and/or adverse event (AE) form.

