#### 8.2 Statistical Methods

8.2.1 The reference (RRref) will be obtained by measuring respiration rate based on manual annotations of respiratory inspirations and expirations. Bias will be reported using the following equation and will be used for each site, subject, and for all data combined:

$$Bias = \frac{1}{n} \sum_{i=1}^{n} (RR_a - RR_{ref})$$

8.2.1.1 Optional analysis may be performed based on the available capnography data collected from subjects who could tolerate the device. The statistical formula for calculating bias for the capnography results will be similar to the above equation but with RRa replaced by respiratory rate from capnography (RRcap).

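### The reference rate is read from the investigational sensor's own recording, so breaths missing from it cannot show as bias; the breath counts have no stated analysis, and the capnography formula leaves out RRa

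*Combined protocol and SAP*

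**What the plan says.** - **Reference.** Section 2.1 (Reference analyzers/methods): "The acoustic raw data collected by the INVSENSOR00004 sensor and Radical 7 pulse co-oximeter will be manually annotated". RRref is calculated from those annotations, and section 8.2.1 repeats this definition.
- **Test value.** Sections 1.2 and 2.1 derive RRa from the acoustic signal of the same INVSENSOR00004 sensor.
- **Outcome.** Section 4.2 reports the bias between "the acoustic respiration rate (RRa) parameter and the manual annotation". Section 8.2.1 gives the formula, the mean of RRa − RRref, by site, by subject and overall.
- **Status of the reference.** Section 4.1 describes it as "actual respiration rates as determined by manual annotation of recorded respiration data".
- **Breath counts.** Under section 7.2.9, "manual breath-counts with the duration of each count will be performed at the start and towards the end of data collection", and "All measurements will be recorded in the CRF". Sections 3, 4.2 and 8 do not mention them.
- **Capnography.** The objective in section 3 compares RRa with the annotated rate "and when applicable with capnography respiration rate", and section 4.1 says the same. Section 8.2.1.1 makes the analysis optional, limits it to subjects who tolerate the device, and gives a formula "similar to the above equation but with RRa replaced by respiratory rate from capnography".
- **Sensor.** Section 1.1 calls the new sensor "similar to the RAS-125c in performance parameters but differs in shape and size". The cleared sensor is for patients above 10 kg; this study concerns those up to 10 kg.

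**The concern.** An error in a respiration monitor can arise in two places. The sensor may fail to pick up a breath, or the algorithm may misread what the sensor picked up. When the reference is annotated from the sensor's own recording, only the second kind can appear in RRa − RRref. Breaths absent from the recording, and sounds that annotator and algorithm both take for breaths, cancel.

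The first kind matters here because the sensor has a new shape and size and is being tried in smaller subjects, at several neck and chest positions (section 7.2.2). A bias near zero could be read as accuracy against true breathing, a reading that section 4.1 encourages by calling the reference the actual rate.

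The plan already collects information that could test capture, but the breath counts are given no analysis, and the capnography formula as written is not the comparison named in the objective.

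**Working it through.** **Inputs from section 8.1.** Equivalence limit δ = 2.0 RPM; SD σ = 3.0 RPM; minimum 18 and maximum 100 subjects.

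**The plan's own figure.** N = ((1.96 + 0.85) × 3 / 2)² = 17.77, rounded up to 18. This reproduces and is not in dispute.

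**Step 1: what cancels.** Let R be the true rate and f the share of breaths leaving no usable trace. If algorithm and annotator both follow the recording, RRa = RRref = (1 − f)R. Then

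- planned bias = RRa − RRref = 0
- error against true breathing = RRa − R = −fR

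The error equals the limit when f = 2.0 / R. The documents give no true rates, so R is assumed:

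| Assumed R (breaths/min) | Share lost that equals 2.0 RPM |
|---|---|
| 30 | 2/30 = 6.7% |
| 40 | 2/40 = 5.0% |
| 60 | 2/60 = 3.3% |

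**Step 2: what the capnography formula shows.** Take R = 40, f = 10%, so RRref = 36, and suppose capnography reads the true 40. Add an algorithm error e, so that RRa = 36 + e:

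| e | RRa − RRref (8.2.1) | RRcap − RRref (8.2.1.1) | RRa − RRcap (objective) |
|---|---|---|---|
| −3 | −3 | +4 | −7 |
| 0 | 0 | +4 | −4 |
| +3 | +3 | +4 | −1 |

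The 8.2.1.1 quantity detects the lost breaths, so it is a useful check on the reference. It contains no RRa term and does not move when RRa changes, so it is not the comparison in sections 3 and 4.1.

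**Step 3: what a count-based check could deliver.** The number and duration of counts cannot be read in the public document. Assumptions: two counts per subject, an independent counting error with an SD of one breath per count, and the 3.0 RPM of section 8.1 as the between-subject SD. One breath in a count of T seconds is 60/T RPM: 4, 2 or 1 RPM at 15, 30 or 60 s. The 95% CI half-width for the mean difference is

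t(0.975, N − 1) × √[(3.0² + (60/T)²/2) / N]

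with t = 2.110 for N = 18 and 1.984 for N = 100.

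| Count length | SD per subject | Half-width, N = 18 | Half-width, N = 100 |
|---|---|---|---|
| 15 s | √(9 + 8) = 4.12 | 2.05 | 0.82 |
| 30 s | √(9 + 2) = 3.32 | 1.65 | 0.66 |
| 60 s | √(9 + 0.5) = 3.08 | 1.53 | 0.61 |
| no counting error | 3.00 | 1.49 | 0.60 |

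Under these assumptions, counts of 30 s or more lose little precision. With 15 s counts and 18 subjects the half-width exceeds the 2.0 RPM limit.

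**The case against.** The strongest reply is that annotation is an openly stated reference. Section 3 sets out to compare RRa with annotated rates, and section 4.1 qualifies its wording by saying how the rate is determined. That stands, and it is why the primary outcome need not change. It does not give the statistic any power to detect missing breaths.

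Full cancellation is also a worst case. An annotator may recognise or exclude a silent stretch, the algorithm may return no value there, and breaths that the annotator identifies but the algorithm misses still appear as bias. This is right, and it makes the loss percentages illustrations rather than estimates.

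On capnography, the mean of RRa − RRcap equals the mean of RRa − RRref minus the mean of RRcap − RRref, so the stated comparison can be recovered by subtraction. This holds only over matched samples, and only if the optional analysis is run. The mismatch between 8.2.1.1 and the objective remains.

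Finally, the precision figures rest on assumed count numbers, durations and errors, and on an SD planned for another comparison. That the counts are independent of the sensor is a reasonable inference, but the protocol does not say how they are made. At the minimum sample size the check is weak. These points limit what the counts can prove; they do not justify leaving them unanalysed.

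**Conclusion.** The concern holds on all three parts, and each can be read directly from the text. RRa and RRref share one recording, so the only firmly planned statistic measures agreement with a human reading of that recording and not signal capture. The breath counts are collected with no stated use. The formula in 8.2.1.1 would not produce the capnography comparison named in sections 3 and 4.1.

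How much error is hidden cannot be known from the documents. The figures of 6.7%, 5.0% and 3.3% assume true rates of 30, 40 and 60 breaths/min and equal loss from RRa and RRref. This should be corrected, but it does not invalidate the primary comparison or the sample size of 18.

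**What to change.** 1. **Section 8.2:** add a prespecified supportive analysis of RRa − manual count and RRref − manual count over time-matched count windows. Report bias, SD and a 95% CI that allows for repeated windows within a subject.
2. **Section 8.2.1.1:** report RRa − RRcap as well as RRcap − RRref wherever capnography was recorded. The first is the stated comparison; the second checks the reference.
3. **Section 4.1 and the study report:** replace the word 'actual' and describe RRa − RRref as agreement with annotation of the same recording.

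The primary outcome and sample size are unchanged. The cost is SAP text and a small extra analysis, with one operational condition: count start times must be on the CRF and aligned with the recording. The documents do not say that they are, so a CRF or procedure change may be needed, and counts already taken without a time could not be matched. Bedside counts carry their own error, so this estimate will be less precise than the annotation-based one and should be presented as supportive.

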#### 2.2 Device Accountability

#### 2.2.1 Receipt of Study Device

Masimo may ship or hand-carry devices and sensors to the investigative sites. Upon receipt of the of the study device supplies, an inventory must be performed and the Equipment Shipment Check Form (FRM-2713) and the device accountability log (FRM-3407) will be completed for each device and signed by the receiver. It is important that the designated study staff counts and verifies that the shipment contains all the items noted in the shipment inventory. Any damaged or unusable study devices in a given shipment will be documented in the study files. The investigator must notify the study sponsor of any damaged or unusable study devices that were supplied to the investigator's site.

#### 2.2.2 Use of Study Device

Use of devices and sensors will be documented on case report forms (CRF) for each subject. Any unused devices must be returned to the Sponsor at the end of the study.

#### 2.2.3 Return or Destruction of Study Device

At the completion of the study, there will be a final reconciliation of study devices. This reconciliation will be logged on the device accountability log. Any discrepancies noted will be investigated, resolved, and documented prior to return or destruction of unused study devices. Devices destroyed on site will only be upon written instruction from the Sponsor and will be documented in the study files.

#### 2.3 Risk/Benefits

**Benefits:** There will be no direct benefits to the enrolled subjects. Future benefits of continuous noninvasive respiration rate monitoring may aid clinicians to predict respiration deterioration in pediatric population in hospitals, hospital-type facilities, mobile, and home environments.

**Sensor risks:** As with all RAM sensors and pulse oximeter sensors there is risk of thermal burn and skin irritation, discomfort, and redness due to the sensor adhesive. The design includes safeguards, and this risk is believed to be low.

All patient-contacting materials, including the adhesive used in the design of the Masimo Rainbow sensors, have been subjected to biocompatibility tests per ISO 10993-1, ISO 10993-5, ISO 10993-10 and results demonstrate that the materials are non-toxic, non-irritating, and non-sensitizing. The sensors have been subjected to performance, mechanical, and electrical testing and results demonstrate that the sensors meet the requirements for safety and effectiveness for the intended use of the product. The modifications to the sensor are specifically designed so as not to introduce any new risks to the subject, and have been developed pursuant to the design control regulations per ISO 14971.

#### 3 STUDY OBJECTIVES

The objective of this clinical investigational study is to compare the acoustic respiration rates (RRa) obtained using the INVSENSOR0004 sensor in the subjects up to 10 kg with the respiration rates determined by manual annotations (RRref), and when applicable with capnography respiration rate (RRcap).

#### 4 STUDY DESIGN

#### 4.1 General Design

This is a multi-center, prospective and nonrandomized study design. RRa measurements will be compared to measurements of actual respiration rates as determined by manual annotation of recorded respiration data, and when applicable to capnography data.

#### 4.2 Study Outcome and Measurement

Evaluation on the comparison of RRa measurements will be reported as a bias of between the acoustic respiration rate (RRa) parameter and the manual annotation (RRref).

#### 5 CLINICAL SITES

This is a multicenter study that may enroll up to 100 total subjects. The subjects enrolled in this study may be recruited from the following sites:

Site	Site Name and PI	Site Description
1	Children's Medical Center Dallas (CMCD)	Children's Hospital (Pediatric Anesthesiology)
	Dallas, TX	
2	Loma Linda University (LLU)	Department of Anesthesiology
	Loma Linda, CA	

#### **6 SUBJECT SELECTION AND WITHDRAWAL**

#### 6.1 Population Base

Subjects will be healthy and non-healthy subjects. Subjects will be recruited from diversified demographics (age, gender, ethnicity, skin tone, comorbidities, etc).

#### 6.2 Inclusion Criteria

- Subject weighing up to 10 kg
- Subjects will be inpatients and/or outpatients admitted in the NICU or PICU or PACU
- The parent/legal guardian has given written informed consent/assent to participate in the study

#### 6.3 Exclusion Criteria

- Subjects with underdeveloped skin
- Subjects with skin abnormalities at the planned application sites that may interfere with sensor application, per directions-for-use (DFU) or trans-illumination of the site, such as burns, scar tissue, infections, abnormalities, etc.
- Subjects deemed not suitable for the study at the discretion of the investigator

#### 6.4 Subject Recruitment and Screening

Following identification of a potential subject, the patient will be approached by either the principal investigator or a designated research study staff (co-investigator and/or study coordinator), who will explain the purpose and procedures of the study. If the patient expresses an interest in participating in the study, they will be asked to read the Informed Consent Form.

All subjects will have their medical history reviewed at the time of screening, after informed consent has been obtained, by either the PI or the study staff who is delegated for this task. Subjects will be evaluated based on the inclusion and exclusion criteria to determine eligibility to be enrolled into the study. If a subject is deemed ineligible after screening, the subject will not be enrolled in the study. If the subject meets all of the inclusion and none of the exclusion criteria, the subject will be enrolled into the study.

Information regarding the subject's demographics (including, but not limited to age, weight, race, ethnicity, comorbidities, medications, etc.), preexisting allergies, skin abnormalities and other preexisting diseases/conditions that may be relevant to the study will be recorded within the CRF.

#### 6.4.1 HIPAA

The pre-screening of patients will require the investigators to access personal health information to identify prospective subjects without HIPAA authorization prior to obtaining written informed consent for the study. Informed consent and HIPAA authorization will be obtained during recruitment and screening procedures as described in previous sections of this clinical investigation plan; however, pre-screening process would require a waiver of HIPAA authorization, as the research study could not be practicably carried out without this implied waiver of consent. The participants' rights and welfare will not be adversely affected by waiving consent. Patients' protected health information (PHI) will not be inappropriately reused or disclosed to any other person or entity. To further safeguard all protected health information, the data collected during the study will not be labeled with any personal identifying information, or with a code that this research team can link to personal identifying information. The data will not be stored with any protected health information identifiers.

